5.7 Supportive Care

5.7.1 All supportive measures consistent with optimal patient care will be given throughout the study per investigator discretion or institutional guidelines.

- Skin: Encourage good skin care
 - Regular use of topical emollients
 - Avoid unnecessary exposure to sunlight, apply broad spectrum sunscreen and/or sun protective clothing
 - Topical steroids or topical antibiotics may be applied to affected areas as needed (mild-strength topical steroid (hydrocortisone 1% cream) or topical antibiotic (e.g. clindamycin) or oral antibiotics
- Gastrointestinal:
 - Antiemetic and anti-diarrheal agents may be prescribed per investigator or institutional guidelines.

5.8 Duration of Therapy

Neoadjuvant Phase: 8 weeks (2 cycles)

Adjuvant Phase: 44 weeks (11 cycles)

Patients will receive protocol therapy unless:

- New progressive lesions are seen on post neoadjuvant treatment CT, MRI and/or PET scans and confirmed as distant metastatic disease.

- If a new/progressive lesion is noted on imaging after neoadjuvant therapy, histologic evaluation with a biopsy is required to confirm disease progression, unless the lesion is not accessible or a biopsy would cause undue risk to the patient.
- If the progressive disease is still considered eligible for a complete surgical resection, the patient may proceed on to surgery per investigator discretion and a biopsy is not required before surgery.
- If pathology review of surgical specimen confirms progressive disease, these patients will then come off study treatment and not receive the adjuvant phase of therapy, and will be followed for survival.
- If pathology review of surgical specimen shows treatment effect, these patients will continue on study and receive adjuvant phase of therapy.
 - If the progressive disease is not considered resectable based on post treatment scans, biopsy, and surgical consultation/opinion, surgical resection will not be carried out and the patient will be off study treatment and followed for survival.

NOTE: All patients who received at least one dose of neoadjuvant therapy are expected to complete post FLT PET/CT regardless of radiologic, clinical or pathologic response and prior to coming off study treatment. **If a patient comes off treatment early the second ¹⁸F-FLT PET/CT scan should not be completed any sooner than four weeks after starting neoadjuvant therapy.**

NOTE: Date of neoadjuvant progression will be the earliest date of confirmed progression before surgery.

Additional Reasons for Treatment Discontinuation

- Extraordinary Medical Circumstances: If at any time the constraints of this protocol are detrimental to the patient's health, protocol treatment should be discontinued per investigator discretion. In this event submit forms according to the instructions in the EA6183 Forms Packet.
- Patient withdraws consent.
- Patient experiences unacceptable toxicity.
- Non-protocol therapies are administered.
- Progression of disease per RECIST 1.1 before surgery that renders the patient ineligible for surgery.
- Relapse of disease after surgery.
- Treatment delay/hold of greater than > 42 consecutive days for any reason.

NOTE: All reasons for treatment discontinuation must be documented on the case report forms in Medidata Rave.

For this protocol, all patients, including those who discontinue protocol therapy early, will be followed for response until progression, even if non-protocol therapy is initiated, and for survival for 5 years from the date of registration. Patients will

be followed every 3 months for the planned year of treatment and for 1 additional year, then every 6 months for 3 years. All patients must also be followed through completion of all protocol therapy.

- For patients who have confirmed progression per RECIST 1.1 prior to surgery and do not undergo surgery, the patient will come off study treatment and be followed for survival.
- For patients who have confirmed progression per RECIST 1.1 prior to surgery, but are still deemed eligible for surgical resection – they will be followed for progression and survival.
- For patients who come off study treatment for intolerable toxicities at any time, they will be followed for progression and survival. If a patient comes off treatment early for anything other than progression of disease, follow up for the planned year of treatment with scans and H/P will continue at every 3 months.

6. Measurement of Effect

6.1 Antitumor Effect – Solid Tumors

6.1.1 Neoadjuvant Effect – Solid Tumors

- Pathologic response: will be assessed once at approximately 10-12 weeks: following surgery and 8 weeks of systemic therapy as assessed on local review. Central review will be performed retrospectively. The following definitions will be employed: [Tetzlaff, Annal Oncol, 2018]
- Pathologic Complete Response (pCR)
 - Complete absence of viable tumor in the treated tumor bed
- Major PR
 - ≤10% of viable tumor in the treated tumor bed
- Partial Pathologic Response (pPR)
 - Less than or equal to 50% of the treated tumor bed is occupied by viable tumor cells
- Pathologic Non-Response (pNR)
 - Great than 50% of the treated tumor bed is occupied by viable tumor cells
- Radiologic Response: For the purposes of this study, patients should be evaluated for radiologic/clinical response after 8 weeks of therapy but prior to surgery, and then every 12 weeks (+2 weeks) (20 weeks, 32 weeks and 44 weeks and 56 weeks (end of treatment) for one year, then every 12 weeks (+4 weeks) x 1 year, then every 24 weeks (+4 weeks) x 3 (until year 5).

Post-neoadjuvant treatment CT (or MRI) scan of chest, abdomen, pelvis and/or any other involved sites with contrast (unless contraindicated) will be performed and the response to systemic treatment assessed in addition to clinical assessment. Response and progression will be evaluated in this study using the international criteria proposed by the revised Response Evaluation Criteria in Solid Tumors (RECIST) guideline (version 1.1) [Eur J Ca 45:228-247, 2009]. Changes in the largest diameter (unidimensional measurement) of the tumor lesions and the shortest diameter in the case of malignant lymph nodes are used in RECIST. If a new/progressive lesion is noted on imaging after neoadjuvant therapy, histologic evaluation with a biopsy is required unless the lesion is not accessible or a biopsy would cause undue risk to the patient. If the progressive disease is still considered eligible for a complete surgical resection, the patient may proceed onto surgery per investigator discretion and a biopsy is not required before surgery. Pathologic evaluation would then confirm if true disease progression versus treatment effect. If the progressive disease is not considered resectable based on post treatment scans, biopsy, and surgical

consultation/opinion, surgical resection will not be carried out and the patient will be off treatment and followed for survival.

The following general principles must be followed:

2. To assess objective response, it is necessary to estimate the overall tumor burden at baseline to which subsequent measurements will be compared. All baseline evaluations should be performed as closely as possible to the beginning of treatment and never more than four weeks before registration.
3. Measurable disease is defined by the presence of at least one measurable lesion.
4. All measurements should be recorded in metric notation by use of a ruler or calipers.
5. The same method of assessment and the same technique must be used to characterize each identified lesion at baseline and during follow-up.

6.1.2 Definitions

Evaluable for Response

Evaluable patients are defined as eligible patients (per Section 3) who receive at least one dose of neoadjuvant therapy with encorafenib and binimatinib and are resectable at enrollment.

- Patients who do receive treatment but demonstrate progression of disease per RECIST and do not proceed to surgery will be classified as pathologic non response (pNR).
- Patients who receive at least one dose of treatment but do not receive surgery for other reasons will be evaluated for radiographic/clinical response.

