1.8 Hypotheses

1.8.1 Primary

- 1.8.1.1 Neoadjuvant treatment with a combination of binimetinib and encorafenib in Stage IIIB/C/D clinically evident nodal resectable melanoma will yield a pathologic complete response (pCR) rate of at least 57%.
- 1.8.1.2 Summarizing current pCR data (Table1), a weighted average pCR rate for immunotherapy neoadjuvant trials with ranges from 15%-57%, would be 33%. The two small studies of neoadjuvant BRAF + MEK inhibitors have shown response rates of 52% and 58%. It is hypothesized that encorafenib and binimetinib will have a similar response rate as the other BRAF/MEK inhibitors, and greater than that seen with immunotherapies.

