9.1 Study Design and Objectives

In this phase II study, patients with resectable locoregional metastases from cutaneous or unknown primary melanoma (Stages III N1B/C/D) will be enrolled. The primary objective is to evaluate the pCR rate for the neoadjuvant combination of encorafenib and binimatinib. It is hypothesized that this combination of treatment will yield at least 57% pCR rate. Simon's two-stage design will be used, enrolling with up to 42 patients (for 39 evaluable).

Evaluable patients are defined as eligible patients (per Section [3](#)) who receive at least one dose of neoadjuvant therapy with encorafenib and binimatinib and are resectable at enrollment. The likelihood of progression, delay in resection or failure to proceed to surgery during the neoadjuvant period is expected to be very low. Therefore, we expect at least 39 out of 42 patients will be evaluable.

All patients who receive at least one dose of neoadjuvant therapy will be included in the 15 patient-cohort that will trigger the interim analysis.

Secondary clinical endpoints include: i) to evaluate clinical response rate (RR), DFS, OS, ii) to assess correlation of pCR with RR, DFS, OS, iii) to assess safety and toxicity iv) to evaluate CD8+ T cell infiltration in tumor or tumor bed pre, during and post neoadjuvant treatment and the change in CD8+ TIL with neoadjuvant treatment and correlate with clinical response, and v) to compare local review for pathologic response with central pathology review. Secondary imaging endpoints are addressed in Section [9.7](#).

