9.2 Study Endpoints

Of the 42 patients accrued, we expect at least 39 patients will be evaluable. The main analysis for clinical endpoints will be based on 39 evaluable patients. Based on prior studies, it is not expected that there will be significant issues with disease progression or severe toxicities that interfere with planned surgical resection.

A pCR will be defined as the absence of residual viable melanoma in the resected metastasis site as assessed on local pathology review.

Overall Survival (OS) will be defined as the time from enrollment to death from any cause. Patients who have not died will be censored at the date last known to be alive. Disease-Free Survival (DFS) will be defined as the time from complete surgical resection to disease progression or death (whichever occurs first). Patients who are not eligible for resection will not be included in this analysis. Cases who have not had an event will be censored at the date of last disease assessment documenting the patient was free of progression. Progression will be evaluated based on international criteria proposed by the revised Response Evaluation Criteria in Solid Tumors (RECIST) guideline (version 1.1) as described in Section [6](#). Response will be defined by the RECIST guidelines (version 1.1) as described in Section [6](#). Toxicity will be defined using the CTCAE.

Ki-67 IHC in tumor cells will be graded as a percentage of total number of tumor cells with nuclear staining (to the nearest 10%) over 10 high powered fields (at 20X magnification).

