9.3 Sample Size Considerations and Monitoring Plan

A Simon's optimal two-stage design will be used to allow for an interim analysis for futility. Accrual will be held during the interim analysis. Fifteen (for 14 evaluable) subjects will be enrolled and pCR will be assessed. If 5 or fewer subjects achieve a pCR, the trial will be stopped for futility. If greater than 5 subjects achieve a pCR, then the trial will enroll an additional 27 (for 25 evaluable) patients. If 18 or more subjects out of 39 total evaluable subjects achieve a pCR the study will be considered 'positive'. The study was designed to evaluate the pCR rate improving from 33% to 57%. This design provides 87% power with approximately one-sided type I error rate of 0.05 for the primary endpoint.

The hypothesis states that encorafenib with binimatinib will yield a pCR rate of 57%. The baseline pCR rate of 33% was estimated from published values as summarized in Table 1 in Section [1](#) and is thus the null pCR rate.

We anticipate an average accrual of 1-3 patients per month. The first stage analysis will occur when the first 15 patients have a pCR assessed. Under the null pCR rate of 33%, there is 70% chance of stopping the study after the first stage evaluation. Adverse events will be closely monitored during the study.

Interim safety analyses based on the first 15 patients will evaluate:

- Proportion of patients who develop progressive disease per RECIST 1.1 before surgery but proceed with surgical resection
- Proportion of patients who develop progressive disease per RECIST 1.1 before surgery and are unresectable
- Proportion of patients who develop toxicities that delay or prohibit surgery
- Surgical complications as defined by the operating surgeon as being related to surgery or oral therapy, at any point during follow up

We anticipate that the proportion of patients who experience any of the event listed in i) -iv) will be less than 15%. If at least one patient (out of 15 patients) experiences any of the event listed in i) - iv), the proposed treatment will be considered unsafe and the result will be discussed with the ECOG-ACRIN DSMC. The probability of observing at least one patient with the event in i) ii), iii) or iv) is 0.794 if the true event rate is 10% and is 0.913 if the true event rate is 15%.

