9.5 Statistical Analysis Plan

Efficacy endpoints will be analyzed in evaluable patients (as defined in Section 9.1. The primary endpoint of pCR rate will be estimated and 90% CI adjusting for the first stage analysis will be provided. OS and DFS distributions will be estimated using the Kaplan-Meier method. Median OS and DFS will be described with 95% confidence intervals. Clinical response rate (RR) (per RECIST 1.1) will be estimated with 95% confidence interval. Clinical data from unevaluable patients will be summarized separately.

Safety analyses will be conducted on all patients who received at least one dose of trial therapy (i.e., treated patients). Adverse events will be graded using the National Cancer Institute (NCI) Common Terminology Criteria for Adverse Events (CTCAE) version 5.0. All treatment-emergent and baseline adverse events and hematological/biochemical toxicities based on laboratory measurements, as well as drug related AEs, will be summarized by NCI CTCAE v. 5.0 worst grade. The incidence of deaths and treatment-emergent serious adverse events (defined as number of patients experiencing the AE divided by all treated patients) will be summarized. Also, the incidence of adverse events leading to discontinuation of investigational product and/or withdrawal from the study will be summarized and listed. Changes in the CD8 T cell infiltration in tumor or tumor bed pre-, during and post- neoadjuvant treatment will be assessed and summarized using the descriptive statistics. The change in CD8+ TIL between pre-and post-treatment will be compared among patients achieving a pCR vs. no pCR using the Wilcoxon rank sum test. The concordance of pCR assessed based on local review vs. central pathology review will be evaluated. Kendall's Tau test will be used for this comparison.

In the event of missing data, it will be assumed that the data will be missing at random and no imputation will be performed.

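### Does a treated patient who misses surgery for a reason other than progression fall out of the pCR analysis?

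*Combined protocol and SAP*

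**What the plan says.** Sections 6.1.2 and 9.1 define an evaluable patient by three conditions: eligible, at least one dose of neoadjuvant therapy, and resectable at enrollment. Having had surgery is not one of them. Section 6.1.2 then assigns pathologic non-response to patients who progress by RECIST and are not operated on. For the others it says: "Patients who receive at least one dose of treatment but do not receive surgery for other reasons will be evaluated for radiographic/clinical response".

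The primary endpoint is set in Section 9.2: "A pCR will be defined as the absence of residual viable melanoma in the resected metastasis site as assessed on local pathology review". Section 9.5 fixes the analysis set, "Efficacy endpoints will be analyzed in evaluable patients", and closes with a general sentence on missing data: "it will be assumed that the data will be missing at random and no imputation will be performed". The decision rule in Section 9.3 begins "If 18 or more subjects out of 39 total evaluable subjects achieve a pCR", in which case the study is called positive.

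The interim look is described twice. Section 9.1: "All patients who receive at least one dose of neoadjuvant therapy will be included in the 15 patient-cohort that will trigger the interim analysis". Section 9.3: "The first stage analysis will occur when the first 15 patients have a pCR assessed".

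**The concern.** A patient who refuses surgery, or whom toxicity keeps from it, is evaluable but has no resected site in which pCR can be read. No passage states in words that this patient counts as not pCR. An analyst who treated the absent specimen as missing data could use the Section 9.5 sentence to leave the patient out.

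The background section shows that this happens. The 58% benchmark in Section 1.8.1.2 is 7 of 12 operated patients in the randomized dabrafenib-trametinib study (Section 1.4). One further treated patient declined surgery after a partial response; counting that patient gives 7/13 = 53.8%.

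In a single-arm trial designed against a null rate of 33%, dropping patients who are unlikely to be pCR raises the reported rate and its confidence limits. The two interim descriptions also part company as soon as one of the first 15 patients is not operated on.

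**Working it through.** **1. The plan's own figures.** Inputs from Section 9.3: 14 evaluable in stage 1, stop at 5 or fewer pCRs, 39 in total, positive at 18 or more, null 0.33, alternative 0.57. With X1 ~ Bin(14, p):

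- early stop = P(X1 ≤ 5)
- P(positive) = Σ over x = 6..14 of P(X1 = x) · P(Bin(25, p) ≥ 18 − x)

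At p = 0.33 the early stop is 0.699 and the type I error 0.0476. At p = 0.57 the power is 0.873. The stated 70%, approximately 0.05 and 87% are reproduced.

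**2. How many such patients.** The documents give no rate, so this is an assumption. Two precedents in Section 1.4 bound it loosely:

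- 3 of 192 not operated in the pooled analysis (1.6%, any reason, immunotherapy included)
- 1 of 48 treated in the two resectable dabrafenib-trametinib studies (35 + 13 treated, 35 + 12 operated; 2.1%)

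Expected number in 39: 39 × 3/192 = 0.61 and 39 × 1/48 = 0.81. The chance of at least one, 1 − (1 − f)^39, is 46% and 56%; of three or more, 2% and 5%.

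**3. Effect on the decision.** Let k patients be unoperated, keep the cut-off at 18 and replace nobody. An unoperated patient adds no pCR on either reading. In the dropped columns the total becomes 39 − k, with stage 1 left at 14.

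| k | 18/(39 − k) | Type I error: dropped, 33% over all 39 (p = 0.33·39/(39 − k)) | Type I error: dropped, 33% among those assessed | Type I error: counted as not pCR (p = 0.33·(39 − k)/39) |
|---|---|---|---|---|
| 0 | 46.2% | 0.0476 | 0.0476 | 0.0476 |
| 1 | 47.4% | 0.0485 | 0.0380 | 0.0375 |
| 2 | 48.6% | 0.0491 | 0.0297 | 0.0290 |
| 3 | 50.0% | 0.0494 | 0.0225 | 0.0222 |

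The third column is the worst case, in which the dropped patients would never have been pCR. If a single dropped patient falls in stage 1 (13, then 38 in total), the error is 0.034 at p = 0.33 and 0.043 at p = 0.33·39/38. Every entry is below 0.05.

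**4. Effect on the estimate.** With 18 pCRs and one patient dropped, the rate moves by 1.2 points (46.2% to 47.4%). A stage-adjusted 90% interval moves from 33.2–63.1 to 34.0–63.8. Stagewise ordering is assumed here, because Section 9.5 names no method.

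**5. Interim.** With a cut-off of 5, P(X ≤ 5) at p = 0.33 is 0.70 with 14 assessed and 0.63 with 15. That gap does not come from missed surgery: if all 15 dosed patients are operated on and counted, the figure is 0.63 under both sections. It reflects the separate difference between 15 enrolled and 14 evaluable. On the worst-case convention of step 3, one unoperated patient among 15 gives p = 0.33 × 15/14 = 0.354, and the two figures become 0.63 and 0.55.

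**The case for a change.** The strongest case for a change is that some text points towards exclusion. Footnote 1 to the Section 7.2 table warns that a case may become unevaluable without the required tissue, and Section 11.1 ties evaluability to the diagnostic and surgical specimens. Section 9.1 also derives its 39 of 42 from the low chance of not reaching surgery, as if missing surgery made a patient unevaluable. Someone who read it that way could let the three spare places refill the 39. The type I error would then be 0.060, 0.074 or 0.091 for one, two or three refilled places (p = 0.33·(39 + k)/39, unoperated patients never pCR). Dropping three and lowering the cut-off to 17 of 36 would give 0.087.

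Part of this stands: the wording is loose, and the rule for these patients has to be inferred. The rest does not carry. The tissue passages concern submitting specimens for central review, while the primary endpoint is read locally. The definition of evaluable is stated explicitly in two sections and omits surgery, so an unoperated patient takes one of the 39 places. No passage provides for replacement or for a lower cut-off, so the inflated figures describe a different plan. Nor does any passage judge the trial by setting the 90% interval against 33%; the count decides.

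On the interim, Section 9.1 is explicit that every dosed patient belongs to the cohort. The assessment wording in Section 9.3 can be read consistently with it, since unoperated progressors already receive a classification without a specimen.

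The precedents are also thin. The 3 of 192 may include progressors, whom Section 6.1.2 already classifies, and the 1 of 48 is a single patient.

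**Conclusion.** No change is needed. Read together, the evaluable definition, the Section 9.5 analysis set and the Section 9.3 count keep a treated but unoperated patient in the denominator as not pCR. The primary analysis needs only pCR or not pCR, so the lack of one of the finer pathologic grades does not matter. The missing-data sentence is general and removes nobody from the evaluable set. Writing the rule out would record what a competent analyst would do anyway.

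The largest plausible effect is on the reported rate: about one percentage point for one such patient, and 3.8 points (46.2% to 50.0%) for three, which has a 2% to 5% chance at the precedent rates. The pass/fail decision keeps its type I error below 0.05. Counting the patients as not pCR costs some power if 57% holds only among those operated on: 84%, 80% or 75% with one, two or three, against 87% by design. That is the price of the conservative reading the plan already implies.

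This rests on the cut-off staying at 18, no replacement of unoperated evaluable patients, and no more than about three of them in 39.
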